## **9 Statistical methods**

Deviations from methods described in this document might appear. In case of such deviations, the reason for the deviation will be stated in the statistical report.

### **9.1 Statistical and analytical plan**

This statistical analysis plan is based on the study protocol version 3.0 dated 22 May 2018 and describes the statistical analyses to be conducted for the final assessment of the study data.

### **9.2 General methodology**

All data summaries and listings will be performed using the SAS System version 9.4 under Windows 10 PRO operating system. The statistical analysis will be performed by SPARC Consulting, Milan, Italy on behalf of Exom Group, Milan, Italy.

Continuous-scaled variables will be summarized with means, medians, standard deviations, quartiles, and minimum and maximum values. Categorical variables will be summarized using patient counts and percentages.

Two-sided 95% confidence intervals for proportions and means will also be produced, where clinically appropriate.

The statistical testing will be conducted at the  $\alpha$  level of 0.05 (two-sided) unless differently specified (primary end-point analysis). Confidence intervals will be calculated at the confidence level of 95%.

### **9.3 Sample size**

The study has been designed to test the hypothesis that apixaban would be non-inferior to dalteparin with respect to the primary study efficacy outcome.

The criteria for non-inferiority require that the upper limit of the two-sided 95% confidence interval of the Hazard ratio is below the pre-specified margin of 2.00.

With the use of an estimated incidence of the primary efficacy outcome of 7% at 6 months with dalteparin and an upper non-inferiority margin of 2.00 for the hazard ratio, we calculated that we would need to enroll 934 complete patients for the study to have 80% power to show the non-inferiority of apixaban, at a one-sided alpha level of 0.025. This sample will be increased to 1,168 patients to account for up to 20% lost in total patient-years. This estimate is consistent with a drop-out rate of 40% assuming patients discontinued uniformly during the follow-up (mean discontinuation time equal to 3 months).

### **9.4 Rationale for the event rates in the two treatment arms**

#### Recurrence rate for dalteparin treated arm

An event rate of 7% has been chosen according to the findings of the CLOT and of the CATCH trials.

Both studies used a prospective randomized open blinded end-point (PROBE) assessment design, had warfarin as the comparator vs LMWH, the same definition for active cancer, the same inclusion criteria concerning initial thromboembolic events, and the same treatment duration (6 months). Unlike the CLOT trial, in which dalteparin was given at a reduced dose after the first month, tinzaparin was given at a full dose throughout the study period in the CATCH study. The primary composite efficacy outcome was symptomatic recurrent VTE in the CLOT trial and symptomatic

recurrent VTE plus unsuspected VTE in the CATCH trial.

Reported incidence rates of recurrent VTE with LMWH were slightly different between the two studies, being 8.0% with Dalteparin in the CLOT study and 7.2% with Tinzaparin in the context of the CATCH trial. The incidence of recurrent VTE was higher in patients receiving warfarin in the CLOT trial (15.8%) than in the CATCH trial (10.5%); a risk reduction for recurrent VTE with LMWH as compared with warfarin of 52% and 35% was reported in the two studies, respectively. The 6-month mortality was lower in CATCH compared with CLOT (32% vs 40%).

The lower risk for recurrent VTE observed in the CATCH trial may reflect differences in patient populations between the two studies. The prevalence of risk factors for recurrent thrombosis was lower in the CATCH as compared to the CLOT population and in particular fewer patients had metastatic disease (55% in CATCH vs 67% in CLOT), an ECOG performance status of 2 (23% for CATCH vs 36% for CLOT); less patients in the CATCH study received anticancer therapy (53% vs 78%), and had a previous history of thrombosis (6% vs 11%) compared with CLOT study. Moreover, differences in primary tumor sites and associated anticancer treatments, and the 10-year time gap between the 2 trials (during which cancer treatments have evolved) might also have contributed to the different risk for recurrent VTE.

From the timing context point of view, our patient population is presumed to be closer to that of the CATCH study (published in 2015) than to the CLOT study (published in 2003). So, it is plausible that patients enrolled in the Caravaggio study will receive less thrombogenic anticancer chemotherapy and improved disease management, as well as they will have less frequently a metastatic disease, due to an earlier diagnosis (screening improvement), like in the CATCH trial.

As a further support to our study hypothesis, the ONCENOX trial, published in 2006, compared Enoxaparin (1.0 mg/kg bid for 5 days + warfarin for 6 months) vs Enoxaparin (1.0 mg/kg bid for 5 days followed by Enoxaparin 1.0 mg/kg od) (low dose – LD) vs Enoxaparin (1.5 mg/kg od (high dose - HD) for 6 months) (13). The study was small with limited statistical power, and recurrent VTE was only a secondary objective. However, the rate of this endpoint was 6.9% with the LD and 6.3% with the HD of enoxaparin, therefore comparable to that observed in the CATCH trial.

#### Recurrence rate for apixaban treated arm

In a post hoc analysis of the Amplify study, 169 patients (3.1%) had active cancer at baseline and 365 (6.8%) had a history of cancer without active cancer at baseline. Among patients with active cancer, recurrent VTE occurred in 3.7% and 6.4% of evaluable patients in the apixaban and enoxaparin/warfarin groups, respectively (relative risk 0.56, 95% confidence interval 0.13-2.37). Among patients with a history of cancer, recurrent VTE occurred in 1.1% and 6.3% of evaluable patients in the apixaban and enoxaparin/warfarin groups, respectively (relative risk 0.17, 95% confidence interval 0.04-0.78). Based on these figures, and taking into account that in the present study more patients with active cancer will be included, it is expected that the recurrent VTE rate in the apixaban treated patients will not be higher than the 7-8% observed in the LMWH treated groups in CLOT and CATCH studies.

#### **9.5 Rationale for non-inferiority margin (delta) choice**

The goal of this trial is to test a drug that could lead to the more convenient oral route of administration than the currently recommended LMWH treatment for cancer patients with VTE (14), thus fulfilling a gap within this therapeutic indication. In this situation, the choice of a

relatively “large” delta for efficacy might be accepted in exchange for the possible safety and compliance benefits, provided that a putative superiority to placebo is not left in doubt (*EMEA/CPMP/EWP/2158/99 Document. Guideline on the choice of non-inferiority margin. July 27, 2005*). Based on these assumptions, the upper limit of the two-sided 95% confidence intervals of the Hazard ratio below the pre-specified margin of 2.00 planned for our study seems to us acceptable from a clinical and methodological point of view.

Further, it's worth reminding that the non-inferiority margins used in pivotal trials on VTE therapy with direct oral anticoagulants were the following:

- 1.5 for HOKUSAI-VTE (Edoxaban)
- 1.8 for AMPLIFY (Apixaban)
- 2.0 for EINSTEIN DVT and EINSTEIN PE (Rivaroxaban)
- 2.75 for RECOVER I and II (Dabigatran)

All the above-mentioned studies were considered valid by EMA and FDA for registration of direct oral anticoagulants for the indication “*treatment of VTE*”.

## 9.6 Adjustments for covariates

All Cox's proportional hazard models and the linear effects models for quality of life evaluation will be performed using treatment group, center, symptomatic vs unsuspected VTE and active cancer vs history of cancer and interaction of stratification factors as dummy covariates.

## 9.7 Handling of data, dropouts and missing values

For the Burden score of ACTS scale, no imputation on missing data will be applied if  $\geq 7$  items are incomplete; otherwise, the Burden score is calculated as the mean of the complete items score x 12. For the Benefit score of ACTS scale, no imputation on missing data will be applied if  $\geq 2$  items are incomplete; otherwise, the Burden score is calculated as the mean of the complete items score x 3.

In the situation where the event date is partial or missing, the date will appear partial or missing in the listings, and any corresponding durations will be presented based on the imputations specified in Section 12 “Partial Date Conventions”.

Other missing data will not be replaced.

The number of patients with missing data will be presented under the “Unknown” category.

Missing values will be included in the denominator count when computing percentages.

When continuous data are being summarized, only the non-missing values will be evaluated for computing summary statistics.

## 9.8 Analysis populations

The following analysis populations will be considered in the statistical analysis:

- The enrolled subjects (ENR) set includes all subjects who signed the informed consent form.
- The Intent-to-Treat (ITT) analysis set includes all randomized subjects. Subjects will be categorized to the group to which they were assigned at randomization, regardless of the treatment actually received.
- The modified Intent-to-Treat set (mITT) includes all randomized subjects who received at least one dose of the study drugs (this is the primary efficacy data set). Subjects will be

categorized to the group to which they were assigned at randomization regardless of the treatment actually received.

- The Safety (SAF) Analysis set includes all randomized subjects with at least one documented administration of any study drug.
- The Per Protocol (PP) analysis set will consist of all patients in the ITT analysis set who complete the study fully compliant with the protocol and without any major violation/deviation. Patients in the PP population will be analyzed according to the treatment they actually received. Major protocol violations are the following:
  - Less than 80% or more than 120% compliance with intended study medications;
  - Use of prohibited concomitant medications (see Appendix 1 of the Study Protocol): dual antiplatelet therapy (any two antiplatelet agents including aspirin plus any other oral or IV antiplatelet drug), oral anticoagulants other than study drug, parenteral anticoagulants (if used contrary to protocol specifications), intravenous fibrinolytics, NSAIDs (if taken for  $\geq$  4 days per week);
  - Error in treatment dispensing resulting in a subject being dosed with an incorrect treatment.

The decision whether a protocol deviation is major or not for the classification of patients to the Per-Protocol analysis set will be made case-by case in the blind data review meeting that will be held before the database lock.

## **9.9 Multicenter studies**

Study center is included in each of the analyses described above. To assess center-to-center variability, forest plots will be generated to display the results at each center.

Due to the possibility of small numbers of patients at some study sites, some sites may be combined in order to bring the numbers of patients in each pooled site to at least 12. Upon completion of the study and prior to unblinding, study statisticians in consultation with the Steering Committee will determine the pooling based on enrolment numbers and geographical proximity.

## **9.10 Multiple comparisons/multiplicity**

No adjustment for multiplicity is required for the primary efficacy analysis because it is focused on a single time point (6-month) at which only two treatments are being compared.

## **9.11 Examination of subgroups**

The treatment effects on the primary variable will be characterized for all subgroups outlined in Table 2.

Analyses will be performed on the primary efficacy dataset (mITT) only.

No hypothesis testing will be conducted among the categories of the subgroups.

Statistics presented for each category of the subgroups will include the apixaban-to-comparator Hazard Ratio adjusted for the competing risk of death unrelated to VTE with the associated two- sided 95% CI (by resorting to the Fine & Gray regression model using treatment group, center, symptomatic vs unsuspected VTE, and active cancer vs history of cancer as dummy covariates).

**Table 2: Subgroups**

Grouping Variable	Category
Index event	Proximal DVT PE
Age	< 65 years old ≥ 65 to < 75 years old ≥ 75 years old
Gender	Male Female
BMI at baseline	≤ 25 kg/m  >25-≤30 kg/m  >30 kg/m 
Level of Renal Impairment (by means of creatinine clearance) at baseline	Severe (≤ 30 ml/min) Mild or Moderate (>30-≤ 80 ml/min) Normal (>80 ml/min)
Active Cancer at baseline	Active Cancer Absence of active cancer
Anticancer treatment during the study period	Any CHT/RT No CHT/RT treatment
Symptomatic VTE at Baseline	Symptomatic Unsuspected

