### **10.3 Cancer diagnosis and history**

The following variables on tumor diagnosis and history will be summarized by treatment group with default statistics for all patients in the ITT set:

- Diagnosis of cancer other than basal-cell or squamous-cell carcinoma of the skin or primary tumor or acute leukemia? (Yes / No);
- Intracerebral metastasis? (Yes / No);
- Time of diagnosis (within 6 months before the study inclusion / between 6 months and 2 years before the study inclusion);
- Treatment for cancer (None in the 6 months prior to study inclusion / at study inclusion / during 6 months prior to randomization);
- Recurrent or locally advanced metastatic cancer (Yes / No);
- Time from diagnosis (months), calculated as:  
(Date of screening visit – date of diagnosis + 1) / 30.4.
- Primary Tumor site (Biliary tract / Bladder / Bone-soft tissue / Brain / Breast / Colorectal / Esophagus / Head and neck / Hematological malignancy / Hepatocellular carcinoma / Kidney / Lung / Ovary / Pancreas / Prostate Gland / Skin – Melanoma / Skin – Basal Cell Carcinoma / Skin – Squamous Cell Carcinoma / Stomach / Testicular cancer / Thyroid / Uterus / Other)
- If hematological malignancy:
  - Type of malignancy (Acute lymphocytic leukemia / Chronic lymphocytic leukemia / Acute myeloid leukemia / Chronic myeloid leukemia / Leukemia – other / Non-Hodgkins lymphoma / Hodgkins lymphoma / Multiple myeloma / Other);
    - Complete remission (Yes / No);
- If lung, type of tumor (SCLC / NSCLC / Other)
- Histological type (Adenocarcinoma / Squamous cell carcinoma / Sarcoma / Neuroendocrine / Unknown / Not applicable / Other)
- Staging at study entry (Localized / Regional / Distant / Unknown / Not applicable)

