##### **DVT**

- Specific type of DVT (Symptomatic / Unsuspected);
- Location of DVT (Upper limbs, Vena Cava, Vena iliaca right / Vena iliaca left / Vena iliaca bilateral, Right femoral vein / Left femoral vein / Bilateral femoral vein, Right popliteal vein / Left Popliteal vein / Bilateral Popliteal vein, Right Distal vein / Left Distal vein / Bilateral Distal vein, Other);
- If symptomatic, type of symptoms (Pain, Redness, Calf pain of tenderness, Swelling of extremities, Tenderness along deep vein, Additional relevant DVT findings);
- Confirmatory tests (Compression ultrasonography, Venography, CT Venography, MR Venography, Other);
- Event resulting in discontinuation or interruption of patient's cancer treatment (Yes / No).

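### The anticancer-treatment subgroup in SAP Table 2 is defined after randomization, so its event rates are distorted and its hazard ratios are unprotected if on-study therapy differs by arm

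*SAP*

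**What the plan says.** SAP 9.11 states: "The treatment effects on the primary variable will be characterized for all subgroups outlined in Table 2". One row of Table 2 is "Anticancer treatment during the study period", split into any CHT/RT and no CHT/RT (below, *Any* and *No*). The output is set out as follows: "Statistics presented for each category of the subgroups will include the apixaban-to-comparator Hazard Ratio adjusted for the competing risk of death unrelated to VTE", with a 95% CI from the Fine & Gray model. The section also limits the analysis: "Analyses will be performed on the primary efficacy dataset (mITT) only", and "No hypothesis testing will be conducted among the categories of the subgroups".

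This is the only row that depends on what happens after randomization. BMI, renal function, cancer status ("Active Cancer at baseline") and symptomatic VTE are tied to baseline by label; index event, age and gender are so by nature. The SAP gives no time window, no landmark, no time-dependent handling, and no rule for therapy started after a recurrence.

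Baseline information exists. Protocol 6.4 and Appendix 3 note (c) collect type and timing of chemotherapy, radiotherapy and surgery at screening. SAP 10.3 summarises prior treatment as "None in the 6 months prior to study inclusion / at study inclusion / during 6 months prior to randomization", but without separating the types.

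**The concern.** To enter *Any*, a patient not on therapy at entry must live long enough to start it, and a recurrence may delay or cancel that start. The outcome and the competing event can therefore help to decide the category. Two things follow. First, VTE and death rates differ between the categories even when therapy has no effect on either. Second, the arms within a category are no longer the randomized arms. If allocation influences who starts therapy, each hazard ratio compares patients selected differently by arm.

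Whether the treatment effect holds during chemotherapy is an obvious clinical question in this population. Two hazard ratios and two sets of event counts side by side invite a reader to take any contrast as an effect of chemotherapy.

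**Working it through.** **The plan's own figures.** None is given for this subgroup. The trial-level figures reproduce: events = 4 × (1.960 + 0.842)² / (ln 2)² = 65.35; 65.35 / 0.07 = 933.5, so 934; 934 / 0.80 = 1,167.5, so 1,168.

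**Inputs.** VTE 7% at 6 months (SAP 9.3). Mortality 32% and 53% on anticancer therapy are the CATCH figures in SAP 9.4, borrowed as assumptions. That 50% of the rest would start CHT/RT within 180 days if event-free, that VTE or death prevents a later start, and that CHT/RT does not alter VTE risk are also assumptions.

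**Step 1: event rates, equal starts in both arms.** Constant hazards per 6 months:
- death: D = −ln(0.68) = 0.3857
- start: S = −ln(0.50) = 0.6931
- VTE: V = 0.0869, chosen so that incidence is close to 7%: V/(V+D) × (1 − e^−(V+D)) = 0.0869/0.4726 × 0.3766 = 6.9%

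Among patients untreated at entry, T = V + D + S = 1.1657 and 1 − e^−T = 0.6883.
- VTE before any start: 0.0869/1.1657 × 0.6883 = 0.0513
- start before VTE or death: 0.6931/1.1657 × 0.6883 = 0.4093
- incidence in *No*: 0.0513 / (1 − 0.4093) = **8.7%**
- share in *Any*: 0.53 + 0.47 × 0.4093 = 0.722
- incidence in *Any*: (0.53 × 0.0692 + 0.47 × (0.0692 − 0.0513)) / 0.722 = **6.2%**

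Check: 0.722 × 6.2 + 0.278 × 8.7 = 6.9%. By baseline therapy, both categories give 6.9%.

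Size and direction depend on the assumptions. If only half of recurrences prevent a start, the rates are 6.7% and 7.5%. With 33% mortality, 30% later starters and 53% on therapy at entry, they are 6.5% (*Any*) and 7.8% (*No*) if VTE prevents a start, but 7.2% and 6.7% if it does not. If CHT/RT doubles the VTE hazard, the Step 1 inputs give 7.4% and 5.4%, against 8.2% and 5.3% by baseline therapy.

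**Step 2: hazard ratios, equal starts.** Simulation of 4 million patients per scenario on the Step 1 inputs, with a one-covariate Fine & Gray model in each category:

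| True HR | *Any* | *No* |
|---|---|---|
| 0.6 | 0.60 | 0.61 |
| 1.0 | 1.01 | 1.00 |
| 1.5 | 1.50 | 1.50 |
| 2.0 | 2.00 | 1.97 |

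The selection works alike in both arms and nearly cancels.

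**Step 3: hazard ratios, unequal starts, true HR 1.0.** The start ratio (apixaban to dalteparin) is assumed.

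| Start ratio | *Any* | *No* |
|---|---|---|
| 0.5 | 1.02 | 0.89 |
| 0.7 | 1.01 | 0.94 |
| 1.3 | 0.99 | 1.07 |
| 2.0 | 0.99 | 1.25 |

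Hand check at ratio 2.0: S = 1.3863, T = 1.8589, 1 − e^−T = 0.8442; VTE before start 0.0395; start 0.6295; incidence in *No* 0.0395/0.3705 = 10.7% with apixaban against 8.7% with dalteparin. Then ln(1 − 0.107)/ln(1 − 0.087) = 1.24, close to the fitted 1.25. With 30% on therapy at entry, 80% later starters and ratio 1.5, *No* gives 1.24. Baseline-defined hazard ratios stayed between about 0.985 and 1.01 in these runs.

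**Step 4: precision at N = 1,168.** *No*: 1,168 × 0.277 × 0.087 = 28 events, SE of log HR 2/√28 = 0.38, so the 95% CI is the HR divided and multiplied by 2.1. *Any*: 1,168 × 0.72 × 0.062 = 52 events, factor 1.7. A shift to 0.89 or 1.25 could not be detected in the trial's own data.

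**The case against.** The strongest reply is that the SAP reports only within-category hazard ratios and tests nothing across categories, and Step 2 shows those ratios are sound when the arms use CHT/RT alike. That stands. A reader might infer that the hazard ratios are biased simply because death and recurrence shape the groups; the calculation does not support this. Bias needs a difference between arms in on-study therapy. The documents neither quantify one nor exclude it. The trial is open-label (Protocol 4.1; SAP 6.7). Protocol 6.5.1 notes that gastrointestinal disorders in periods of active chemotherapy may prevent oral dosing, but that shows chemotherapy affecting study drug, not the reverse.

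A reader might also take the SAP 10.9.1.1 item for DVT and PE, "Event resulting in discontinuation or interruption of" the patient's cancer treatment, as proof that the outcome changes the category. It is not. A patient whose on-study therapy is stopped has already received it and stays in *Any*. Only prevention of a first start moves a patient, and that item does not record it.

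Nor can it be said that on-study therapy goes uncollected. The schedule lists cancer treatments at Visit 1 only, but concomitant medication is assessed at follow-up (Protocol 6.4; SAP 10.6), which may capture chemotherapy. No follow-up item for radiotherapy is listed.

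Finally, the on-study row asks a question that the baseline row answers less directly. In a simulation with equal starts, CHT/RT doubling the VTE hazard, and a true HR of 1.0 on therapy and 0.5 off it, the on-study categories returned 1.00 and 0.51; the baseline categories returned 1.00 and 0.70, because some patients untreated at entry start later. That is a real cost of the change, but the advantage rests on equal starts, which cannot be assumed.

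**Conclusion.** The point holds in a limited form. The categories are defined after randomization and are not protected by it. Their event rates are distorted by the definition itself: about 6.2% against 8.7% when the truth is 6.9% in both, under the stated assumptions, with a size and even a direction that vary with them. The hazard ratios are close to unbiased if on-study CHT/RT is the same in both arms, and otherwise can be off by an unknown amount in either direction (0.89 to 1.25 in *No* for a true 1.0, at assumed start ratios of 0.5 to 2.0).

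Patients on CHT/RT on day 1 and continuing are in *Any* under either definition, so the problem is confined to later starters. If therapy itself raises VTE risk and the arms start it unequally, a baseline row also moves (1.07 in the untreated at start ratio 1.5 and a doubled hazard, against 1.12 in *No*). That movement is a consequence of allocation, not an artefact of the grouping.

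The analysis is secondary and untested. Nothing here bears on the primary non-inferiority conclusion or the sample size.

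**What to change.** Replace the Table 2 row with: CHT/RT at baseline (ongoing at inclusion or within the 6 months before randomization / none). Build it from the screening data on type and timing of cancer treatment (Protocol 6.4; Appendix 3 note c). The SAP 10.3 variable will not serve, because it does not separate chemotherapy and radiotherapy from other treatment.

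If on-study therapy is of interest, add it as a labelled exploratory analysis, by landmark at a fixed visit or as a time-dependent covariate. The latter is better fitted in a cause-specific model, since patients who have died stay in the Fine & Gray risk set without a treatment status. State the time window, the data source for radiotherapy, and the handling of therapy started after a recurrence. Tabulate CHT/RT starts by arm, which shows whether the condition for bias is met.

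The cost is one table row and its output shell, with no new data for the baseline version. The drawbacks are that it answers a slightly different question and that its treated category lies wholly within active cancer, which already has a row.
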